One of the promising ways of addressing all the severe asthma phenotypes may be via targeting one of the upstream inflammatory responses of the disease, such as the cytokine thymic stromal lymphopoietin (TSLP)[13]. TSLP is expressed by the airway epithelium in response to both allergic and non-allergic eosinophilic inflammation [14]. Lack of effective therapies for all patients with severe asthma, together with additional hurdles, such as accessibility or eligibility for more

Study Protocol: [OPCG-2005] Biologic Usage Patterns, Clinical Outcomes and Healthcare Resource Utilization (CLEAR)

than one biologic, have led to patients receiving sub-optimal or inappropriate biologics at initiation [11,12]. This can lead to various patterns of use, such as stopping or switching from the first biologic to a second, and in some cases, to a third or fourth biologic as clinicians and patients search deliberately for adequate response.

In an ISAR study on Biologic Utilization (prepublication) most patients (79%; 2791/3531) continued their first biologic, 10% (356/3531) stopped and 11% (384/3531) switched among patients who were followed up for at least a period of 6 months. This pattern was reproduced at the country level, although the ratio of 'stoppers' to 'switchers' varied. The most common reported reasons for stopping or switching a biologic was lack of efficacy benefits and/or adverse events. Disruption to the clinical management of biologics, most likely due to ineffective response and/or inappropriate initiation of the , may lead to a worsening of asthma control and an associated increase in health care utilization. This has yet to be demonstrated in a real-world setting or quantified. In addition, there may be a subgroup that is eligible yet is not reaping the benefits of targeted therapy.

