#### 3.2 STUDY OUTCOMES

The following outcomes measures are measured after index date (follow-up visits).

Table 3 Clinical outcomes of interest for objective 2 of the study

Variable Name	Туре	Description
Number of annualized asthma exacerbations 	Count	Annualized number of exacerbations requiring rescue steroids after index date
Asthma control in the past 4 weeks	Categorical	Categorized as controlled, partly controlled, or uncontrolled according to the GINA Asthma Control Criteria/Asthma Control Questionnaire (ACQ-6)/Asthma Control Test (ACT)
Total dose of oral corticosteroids 	Continuous	Label Dose X Frequency X Duration of Use for maintenance OCS between the index date and date of data extraction
Number of hospital admissions	Count	Annualized number of hospital admissions after index date
Number of emergency room visits	Count	Annualized number of emergency room visits after index date

<sup>3 Total number of exacerbations will be calculated between index date and current visit date

<sup>4 If use of SCS started after the index date, total dose will be calculated between start- and end date of use

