#### **Group comparisons**

The first set of results for the primary and secondary outcomes (section 3.2) will be demonstrated for those that did not initiate a biologic versus those that did (switch, stop, continue) (initiators

Study Protocol: [OPCG-2005] Biologic Usage Patterns, Clinical Outcomes and

Healthcare Resource Utilization (CLEAR)

versus non-initiators). The second set of results will compare the outcome results for patients that stopped or switched versus those that continued.

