**Primary outcome: Exacerbation** 

An asthma exacerbation will be defined as the occurrence of the following events (ERS/ATS task

force definition):

asthma-related hospital attendance/admission primary care consultation; AND/OR

asthma-related A&E attendance; AND/OR

an acute oral corticosteroid course of 3 days or more

separate recordings of exacerbations within a 14 day period will be treated as the

same exacerbation.

A time-to-event analysis will be performed to analyse the association between utilization pattern and time to first exacerbation with right censoring at the time of death, switching, stopping or loss to follow-up. Kaplan-Meier curves will be used to describe event-free survival over time and comparisons. Conditional Cox regression will be performed with time to the first exacerbation as the outcome variable (y) to estimate Hazard Ratios (HR) with 95% confidence intervals (CI) of the main effect. The proportional hazard assumption will be evaluated visually by means of a log-log

plot of survival.

As the dispersion of the exacerbation data is expected to be high and as this outcome is conditional on the duration of follow-up, we may apply a negative binomial regression (NBR) to estimate the reduced rate of exacerbation (y=annual rate of exacerbation). We switch to a count model to take advantage of all exacerbations at follow up. Group comparisons (e.g. gender, BMI, number of biologics available etc.) will be made if interaction between a group and biologic use pattern is found. We will also run a NBR using the total post-therapy/post-ISAR enrolment

exacerbations.

Secondary outcome: Asthma control

By applying a multinomial regression model (ordered), we will assess the probability or odds of the combined categories partially or controlled versus uncontrolled asthma for those that continue

compared to those that do not initiate or switch or stop.

Secondary outcome: long term oral corticosteroid (OCS) dose

20

Study Protocol: [OPCG-2005] Biologic Usage Patterns, Clinical Outcomes and Healthcare Resource Utilization (CLEAR)

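### Initiators are defined as everyone who started a biologic, but the time-to-first-exacerbation analysis censors them at switching or stopping, so it does not estimate the declared initiator versus non-initiator contrast and covers different follow-up from the count models

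*Protocol*

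**What the plan says.** Section 4.2 of the protocol (Group comparisons) names two sets of results. The first is for "those that did not initiate a biologic versus those that did (switch, stop, continue"), so switchers and stoppers belong to the initiator group. The second is described as follows: "The second set of results will compare the outcome results for patients that stopped or switched versus those that continued".

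Under Primary outcome: Exacerbation, the Kaplan-Meier and Cox analysis uses "time to first exacerbation with right censoring at the time of death, switching, stopping or loss to follow-up". The rule is not limited to either comparison.

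The count version of the same outcome has another window. Footnote 3 to Table 3 (section 3.2) says: "Total number of exacerbations will be calculated between index date and current visit date". Section 4.2 gives the reason for counting: "We switch to a count model to take advantage of all exacerbations at follow up". The negative binomial model of the annual rate is optional, while the one on total exacerbations after therapy start or enrolment is a firm commitment. Nothing ends the count at a stop or switch.

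Section 1 (Background) reports that 79% (2791/3531) of initiators continued, 10% (356/3531) stopped and 11% (384/3531) switched. It adds: "The most common reported reasons for stopping or switching a biologic was lack of efficacy benefits and/or adverse events".

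**The concern.** The declared treated group is defined by starting a biologic, whatever happens next. Ending follow-up at the switch or stop changes the question to the hazard of a first exacerbation while still on the first biologic. Non-initiators have nothing to switch or stop, so this extra censoring falls on one side only. A standard Cox model assumes that patients censored at a given time have the same later hazard as those still at risk. When patients commonly leave because the drug did not work or was not tolerated, that assumption is doubtful, and the protocol plans no adjustment for it.

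The count models keep the time after leaving. A reader would take the hazard ratio and the rate ratio as two views of one contrast, although they cover different follow-up. The section on health resource utilization says that hospital and emergency visits will be examined in the same way as exacerbations, so the mismatch carries over to them.

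**Working it through.** **Share affected.** From section 1: 2791 + 356 + 384 = 3531, and 2791/3531 = 79.0%, 356/3531 = 10.1%, 384/3531 = 10.9%. The protocol's percentages reproduce. Leavers (stop or switch): (356 + 384)/3531 = 740/3531 = 21.0%. These come from an earlier registry study with at least 6 months of follow-up; I assume that the share carries over.

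**What must be assumed.** The protocol gives no exacerbation rates, effect size, time to leaving or length of follow-up for this analysis. The hazard ratios below therefore show direction and rough size only. Matching was not simulated.

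**Simulation 1 (with frailty).** Groups 1:1, gamma frailty, two-year follow-up, 21% of initiators leaving at 4 to 12 months. The rate ratio against non-initiators is 0.5 in continuers and 1.0 in leavers, both before and after they leave.

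| Non-initiator rate per year | HR, full follow-up | HR, censored at leaving | Difference |
|---|---|---|---|
| 0.5 | 0.64 | 0.60 | -0.04 |
| 1.0 | 0.66 | 0.63 | -0.03 |
| 1.5 | 0.67 | 0.65 | -0.02 |

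If instead the second treatment works as well as the first does in continuers (rate ratio 1.0 before leaving, 0.5 after), full versus censored is 0.593 vs 0.600, 0.624 vs 0.631 and 0.646 vs 0.653. Censoring then raises the hazard ratio by about 0.01. If leavers resemble continuers throughout, the shift is near zero.

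The event-rate ratio for the table's scenario follows directly:
- Full window: 0.79 × 0.5 + 0.21 × 1.0 = 0.605.
- On first biologic only, with mean time to leaving (4 + 12)/2 = 8 months = 0.667 years: (0.79 × 0.5 × 2 + 0.21 × 1.0 × 0.667)/(0.79 × 2 + 0.21 × 0.667) = 0.930/1.720 = 0.54.

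**Simulation 2 (constant hazards, no frailty).** 400,000 per group, non-initiators 1.0 per year, continuers 0.6, two years, mean 0.75 years to leaving unless stated.

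| Leavers' rate before, after | HR censored | HR full | Rate ratio, full window |
|---|---|---|---|
| 0.6, 0.6 (uninformative) | 0.600 | 0.600 | 0.600 |
| 1.0, 1.0 | 0.637 | 0.666 | 0.683 |
| 1.5, 1.5 | 0.670 | 0.716 | 0.788 |
| 1.5, 1.5, mean 0.35 years to leaving | 0.647 | 0.716 | 0.788 |
| 1.5, 1.5, all rates halved | 0.670 | 0.740 | 0.788 |
| 1.0, 1.5 | 0.637 | 0.692 | 0.752 |
| 0.6, 1.0 | 0.600 | 0.636 | 0.654 |
| 1.5, 0.6 (second biologic works) | 0.670 | 0.664 | 0.665 |

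The change due to censoring runs from 0.670 - 0.740 = -0.070 to 0.670 - 0.664 = +0.006.

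**Why the effect is limited.** The analysis is of first events, and leavers stay at risk until they leave. In simulation 2, 30% to 53% of leavers had their first exacerbation before leaving. In the scenario tabulated for simulation 1, 47% to 65% of leavers' first events within two years came before leaving. All of these are counted.

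**The case against.** The strongest reply is that a first-event, on-treatment analysis beside an all-events count is a recognised pairing, and that the protocol gives a reason for the count model. Choosing between the windows is then partly a choice of estimand. That is fair as far as it goes. But the stated reason is to use more events, not to answer a different question, and the declared initiator group includes those who switch or stop. The Cox rule conflicts with that definition whichever estimand one prefers.

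A reader might infer stronger claims that the documents do not support:

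- *The hazard ratio is biased in favour of initiating.* This needs a higher hazard after leaving than among initiators still at risk. The protocol gives no such figure, names adverse events as well as lack of efficacy, and gives no split. More than half of leavers are switchers (384 of 740, 52%), so a second biologic that works is no fringe case, and there the shift reverses slightly.
- *Failing initiators are removed.* Only their time after leaving is lost.
- *Any gap between hazard ratio and rate ratio shows this bias.* In simulation 1 the full-window rate ratio is about 0.60 to 0.61, nearer to the censored hazard ratios than to the uncensored ones, because frailty also attenuates a first-event hazard ratio. The two effects cannot be separated by comparing these estimates.
- *There are two primary analyses.* The protocol names one primary outcome, and one of its two count models is optional.

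The size is also modest. In simulation 1 the shift is 0.7 to 1.3 standard errors for 4,000 patients split 1:1, and 0.2 to 0.5 if the rate ratio after leaving is 0.7. Section 2.4 reports 3,532 eligible patients, mostly continuing initiators, and section 4.2 envisages matching. The real standard error would be larger and the shift in those units smaller.

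**Conclusion.** The point holds as a conflict between two stated rules: the initiator group includes switchers and stoppers, while the time-to-event analysis ends their follow-up at the switch or stop. The extra censoring can affect about 21% of initiators and no non-initiators, and it is plausibly informative on the protocol's own account. The firm count model of the same outcome covers different follow-up, and the protocol neither says so nor says which analysis leads.

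The consequence for the hazard ratio depends on how leavers fare afterwards. It is likely to favour initiation if they keep doing badly: about 0.02 to 0.04 lower with two-year follow-up and frailty, up to about 0.07 in the harsher constant-hazard scenarios. It is essentially unchanged if leaving is uninformative, and about 0.01 higher if the second biologic works. All these sizes rest on assumed rates. The problem should be corrected because it is avoidable and the estimate should match the declared contrast, not because a large bias has been shown.

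**What to change.** For initiators versus non-initiators, follow both groups to death, loss to follow-up or last visit in the main Cox analysis and in the count models, and state that common window in sections 3.2 and 4.2. Keep the version censored at switching or stopping as a sensitivity analysis. Label it as an on-first-biologic estimate, with inverse-probability-of-censoring weights built from measured predictors of leaving.

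The same censoring sentence also governs the stopped-or-switched versus continued comparison, where patients would be censored at the event that defines their group. Its window should be stated separately in the same edit.

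The cost is a change of wording and one re-run. The main estimate may come out slightly less favourable to initiation, and it will mix in the effect of later treatment, as a contrast defined by starting a biologic must. The weights can only correct for predictors of leaving that the registry records.

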#### Initiated

- Continued: use of first biologic for at least 6 months, without indication of stopping or switching
- **Switched**: stopped the initial biologic and received a (one or more) different biologic, without restriction of any time lapse between biologics
- **Stopped**: stopped the initial biologic and did not receive another biologic. Caution will be taken as stoppers maybe on the path to switchers. Therefore, data will be reviewed to add a feasible follow-up time post stopping and free of not starting another biologic to ascertain true stoppers.

Study Protocol: [OPCG-2005] Biologic Usage Patterns, Clinical Outcomes and Healthcare Resource Utilization (CLEAR)

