#### Did not initiate:

- Not eligible: Did not meet the criteria for eligibility of biologic therapy and did not initiate any therapy
- Eligible: Eligible for biologic therapy but did not initiate any biologic therapy
- A "frequent-eligibility" criterion of each biologic class will be used to assess eligibility. This
  criterion will be constructed using the results from the ISAR biologic availability survey and
  will be subject to confirmation from the ISAR scientific steering committee (see Table 1 for
  possible criteria per biologic class)

[figure not shown]

Table 1: Frequent-Eligibility Criteria per Biologic Class. Patients who did not initiate biologic therapy and are eligible will meet any of the three criteria for any of the three biologic groups.

	Anti-lgE	Anti-IL5/5R	Anti-IL4/13
Background therapy	Met via ISAR inclusion criteria		
Positive Allergen test	Yes, AND	N/A	N/A
IgE levels	≥ 30 IU/mL, AND	N/A	N/A
BEC	N/A	≥ 150 cells/µL with long- term OCS, OR ≥ 300 cells/µL without long-term OCS, AND	≥150 cells/µL with long-term OCS, OR ≥300 cells/µL without long-term OCS, OR
FeNO	N/A	N/A	≥25 ppb, AND
Exacerbation OR Iong-term OCS	Pre-therapy exacerbation (≥2) OR On long-term OCS	Pre-therapy exacerbation (≥2) OR On long-term OCS	Pre-therapy exacerbation (≥2) OR On long-term OCS

The ISAR enrolment date will mark the start of the outcome period for those who did not initiate biologics while for those who did the index date will be signified by the First Biologic Therapy Start Date. A minimum of 16-weeks of follow-up time post biologic initiation (outcome period) will be applied in alignment with the ERS recommendation for time of biologic response assessment [8]. This is also congruent with the methodology used in the ISAR research project 'Defining and Characterizing Responders to Biologic TrEAtment in Severe AsthMa Patients (BEAM).' To assess the impact of this design, the study will evaluate and report the number of patients that had three types of follow-up data: 1.) <24 weeks, 2.) > 24 weeks to 1-year 3.) >1-year.

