# 3.STUDY VARIABLES AND STUDY OUTCOMES

Values captured closest to, and at/before index date of the following variables will be used to describe the biologic utilization groups (objective 1). Again, the index date refers to the date at which the initiation biologic was started or the date of ISAR enrolment for those who did not initiate any biologics.

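### In stopped or switched versus continued, the Cox analysis censors at the change that defines the group, so its hazard ratio cannot reflect any effect of switching or stopping

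*Protocol*

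**What the plan says.** - **Clock.** Protocol section 2.2 starts the outcome period of non-initiators at registry enrolment, while "for those who did the index date will be signified by the First Biologic Therapy Start Date". Section 3 repeats that "the index date refers to the date at which the initiation biologic was started", and section 3.2 measures all outcomes after that date.
- **Groups.** Section 2.2 defines continued as "use of first biologic for at least 6 months, without indication of stopping or switching". Switched and stopped are defined by leaving the first biologic, with or without a later one. All three labels depend on what happens after the index date.
- **Contrast.** Section 4.2, Group comparisons: "The second set of results will compare the outcome results for patients that stopped or switched versus those that continued". The first set compares initiators with non-initiators.
- **Model.** Section 4.2, Primary outcome, uses Kaplan-Meier curves and conditional Cox regression to relate utilization pattern to "time to first exacerbation with right censoring at the time of death, switching, stopping or loss to follow-up". An annual-rate negative binomial model is optional. A second negative binomial model, on all exacerbations after index, is planned outright.
- **Other outcomes.** Hospital and emergency visits are to be examined in a similar way to the primary outcome.
- **Reasons for change.** Section 1 reports that in an earlier registry study the commonest reasons for stopping or switching were "lack of efficacy benefits and/or adverse events".

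**The concern.** The subtitle asks for the effects of continuing, switching and stopping, and the Background supposes that disruption of biologic treatment worsens control. That question concerns what happens after the change. The Cox analysis closes each switcher's and stopper's record at the change, so what it compares is how patients fared on the first biologic before some of them changed. If exacerbations on the first biologic help to bring about the change, the later changers will show a higher hazard even when changing does nothing. A reader would take that HR as harm from switching or stopping.

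**Working it through.** **1. The rules side by side**

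| Group | Label fixed by | Clock starts | Record closed by the rule at | Treatment during analysed time |
|---|---|---|---|---|
| Continued | no change seen | first biologic | death or loss | first biologic |
| Switched | later switch | first biologic | the switch | first biologic |
| Stopped | later stop | first biologic | the stop | first biologic |

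Among initiators, censoring at a change falls only on the groups whose effect is sought. Section 2.2 also plans to require follow-up after stopping to confirm true stoppers. The Cox analysis then discards that follow-up.

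**2. Why the HR cannot respond to the effect**

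Let T be the time to first exacerbation, S the time of change and C other censoring, all from the first biologic. Let the hazard be λ before S and θλ after it, so that θ is the effect of the change. Cox regression uses X = min(T, S, C) and the indicator D = 1 if T ≤ min(S, C). Neither X nor D depends on anything after S, so θ does not enter the likelihood. This step needs no assumed rates.

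**3. Figures in the protocol**

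The protocol gives no HR, event count or power for this analysis. The group shares in section 1 reproduce: 2791 + 356 + 384 = 3531, that is 79.0%, 10.1% and 10.9%. Patients who changed: (356 + 384)/3531 = 740/3531 = 21.0%.

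**4. Simulation with a known effect**

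All rates are assumptions: 40,000 initiators, weekly steps, 2 years, 1 exacerbation per patient-year, and no heterogeneity between patients. The switch hazard is 0.06 per year, multiplied by m in the 26 weeks after an exacerbation. True θ is 0.5, 1.0 or 1.5.

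| m | Share switched | HR as written (same for all three θ) | HR with clock at the switch (θ = 0.5 / 1.0 / 1.5) |
|---|---|---|---|
| 1 | 11.2% | 0.992 | 0.522 / 1.007 / 1.528 |
| 2 | 14.7% | 1.227 | 0.525 / 1.024 / 1.550 |
| 4 | 21.5% | 1.525 | 0.521 / 1.014 / 1.529 |
| 8 | 32.6% | 1.863 | 0.521 / 1.025 / 1.535 |

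The as-written HR moves only with m. In the last column, each switcher is compared with a patient still on the first biologic at the same time since initiation.

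**5. Size under no true effect, with 21% changing**

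Assumed: mean 1 exacerbation per year, follow-up uniform from 0.5 to 5 years, and a 3-month window after an exacerbation. The as-written HR for m = 1, 2, 4, 8 was:

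- no heterogeneity (the limit in which baseline matching removes it all): 1.01, 1.11, 1.22, 1.31
- gamma heterogeneity of variance 1, unmatched: 0.99, 1.22, 1.54, 1.94

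A further set of null runs with 21% changing gave 0.99 to 1.30 and 1.03 to 1.92 respectively. The plan's matched model should fall between the two cases. The size also depends on the window and the follow-up: step 4 has no heterogeneity but a 26-week window over 2 years, and it gave larger values than the first line here.

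**6. Is moving the clock enough?**

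Under heterogeneity and no true effect, moving the clock to the change without updating covariates still gave 1.10, 1.23 and 1.41 for m = 2, 4, 8 (about 1.12 to 1.40 in the further set). Matching also on exacerbations since initiation gave 0.98 to 1.00 (about 1.03 to 1.04 in the further set). The good recovery in step 4 relies on homogeneous patients.

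**The case against.** - **The time origin is not restated beside the Cox model, and the design figure is not available.** True, but sections 2.2, 3 and 3.2 fix it. A clock starting at the change would not rescue the text either: with censoring at stopping, stoppers would have no follow-up.
- **Not every primary-outcome analysis loses the later time.** This stands. A reader might infer that all post-change events are discarded, but the negative binomial model on all exacerbations after index keeps them. Its fault is different: it credits events before the change to the switched or stopped group.
- **A reader might infer that the whole primary analysis fails.** The documents do not support that. For initiators versus non-initiators, censoring at a change is an analysis on first treatment. It is interpretable, though the censoring is likely to be informative.
- **A reader might infer that patients change mostly for lack of efficacy, so that changing must look harmful.** The Background names lack of efficacy and/or adverse events and gives no split. Changes for adverse events need not follow exacerbations, and at m = 1 the HR is about 1.0.
- **Matching and adjustment will deal with it.** Only in part. They can reduce baseline heterogeneity, and much of the larger bias in step 5 comes from that. They cannot balance exacerbations that occur after baseline, and no matching restores the missing post-change time.
- **A SAP may settle it.** The point is a censoring rule that the protocol states, and it conflicts with the protocol's own contrast.

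**Conclusion.** The point holds for stopped or switched versus continued. That the Cox HR is blind to any effect of switching or stopping follows from the stated clock and censoring rule alone. The upward bias is conditional on exacerbations prompting the change, which the reported reasons make plausible but do not quantify. Its size, about 1.0 to 1.9 under no true effect, rests on assumed rates, multipliers, windows and heterogeneity. It should not be read as what the plan's matched model will return. The negative binomial models do not isolate the effect either, and hospital and emergency visits inherit the problem because they are analysed similarly. This should be corrected before the analysis, since the contrast is the subject of the study's subtitle.

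**What to change.** For switch versus continue and stop versus continue:

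1. Set time zero at the switch or stop date.
2. Match each such patient to patients still on their first biologic at the same time since initiation, using covariates updated to that date: exacerbations since initiation, asthma control and long-term OCS.
3. Remove switching or stopping as a censoring event for the patient whose group it defines, and state how comparators who later change are handled.
4. Count exacerbations, admissions and emergency visits only from that time zero. Report earlier events descriptively.

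A model with biologic status as a time-varying exposure is acceptable only if it also adjusts for the updated exacerbation history.

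**Cost.** The change itself is protocol or SAP wording and code. Table S1 lists start and end dates for anti-IgE and anti-IL-5 therapy. It does not name them for anti-IL4/13, although a footnote says new biologics will be added, so this needs checking. Exacerbation dates and OCS doses are bolt-on variables (Table S2), and the minimum follow-up in section 2.1 runs from initiation, not from the change. Patients without those data, or with little follow-up after the change, will contribute less or be lost, so precision for this contrast falls.

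### The primary exacerbation outcome is defined as a count, but the first firm analysis is time to first exacerbation, the annual-rate model is optional, and none of the three planned analyses is named primary

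*Protocol*

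**What the plan says.** Protocol section 1.2, Objective 2, gives reduction of exacerbations as its first example of a clinical outcome. Section 3.2, Table 3, types the exacerbation variable as a count and describes it as "Annualized number of exacerbations requiring rescue steroids after index date".

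Section 4.2, under the primary outcome heading, sets out three analyses:

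1. Kaplan-Meier curves and a Cox model, worded firmly: "Conditional Cox regression will be performed with time to the first exacerbation as the outcome variable (y"). It yields hazard ratios with 95% confidence intervals and has "right censoring at the time of death, switching, stopping or loss to follow-up".
2. A model of the annual rate, worded as optional: "we may apply a negative binomial regression (NBR) to estimate the reduced rate of exacerbation". The reasons given are that outcome depends on length of follow-up and that dispersion is expected to be large: "As the dispersion of the exacerbation data is expected to be high". The text continues: "We switch to a count model to take advantage of all exacerbations at follow up".
3. A model of the total count, worded firmly: "We will also run a NBR using the total post-therapy/post-ISAR enrolment" exacerbations. No offset or other follow-up adjustment is given for it.

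No sentence says which of the three is primary. The health resource utilization paragraph of section 4.2 then says that hospital and emergency room visits will be examined in a similar way to the primary outcome.

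**The concern.** The objective and the outcome table are about how many exacerbations patients have. A time-to-first analysis asks how soon the first one occurs and ignores the rest. The protocol recognises this, since it brings in the count model in order to use every event, yet the only model it describes as a rate is the one left optional. The firm count model is introduced as an addition. Without a stated follow-up term it does not estimate a rate when follow-up differs between patients, and it will differ: section 2.1 sets only a 24-week minimum, and section 2.2 plans bands running beyond one year.

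Two things are at stake. First, if the Cox and count models disagree, nothing in the protocol says which answers the primary question. The section 9 timeline puts analysis and pilot results in May to August 2021 and protocol finalization in August 2021, so precedence should be fixed in writing. Second, with strong between-patient heterogeneity the first-event hazard ratio understates the rate ratio and is estimated from fewer events. The same ambiguity passes to the hospital and emergency room counts.

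**Working it through.** **No plan figure to reproduce.** The protocol has no sample-size, event or power calculation. The only related figures are the group sizes from the earlier ISAR utilization study in the Background: 2791 + 356 + 384 = 3531, i.e. 79.0%, 10.1% and 10.9%, in line with the stated percentages.

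**Inputs.**
- From the protocol: 24-week minimum follow-up (section 2.1); significance at p < 0.05 (section 4.1), taken as two-sided; 356 stoppers (Background), used as n = 356 per arm for a 1:1 matched comparison.
- Assumed, because the protocol is silent: reference rate μ = 0.5 to 3 per year; dispersion k = 0.5 to 2; follow-up T = 24 weeks, 1 year or 2 years; true rate ratio RR = 1.25.

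**Model.** Events follow a Poisson process with gamma-distributed patient effects, which gives negative binomial counts.
- Probability of at least one event: F(μ) = 1 − (1 + kμT)^(−1/k).
- First events as a share of all events: F(μ)/(μT).
- Large-sample Cox hazard ratio: solved numerically from the score equation, with marginal hazard μ/(1 + kμt) in each arm.
- Cox power: Φ(½√d · log HR − 1.96), where d is the number of first events.
- Negative binomial power: Φ(log RR/SE − 1.96), where SE² = [1/(μ·RR·T) + k + 1/(μT) + k]/n.

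**Central case: μ = 1, k = 1, T = 1.**
- F = 0.500 and 0.556, so d = 356 × 1.056 ≈ 376 first events out of 356 × 2.25 = 801 expected events.
- HR ≈ 1.178; log-scale attenuation is 1 − log(1.178)/log(1.25) ≈ 26%.
- Cox: ½√376 × log HR ≈ 1.59, power ≈ 36%.
- Negative binomial: SE² = 3.8/356 = 0.01067, SE = 0.1033, 0.2231/0.1033 = 2.16, power ≈ 58%.

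**Other cases (n = 356 per arm, RR = 1.25).**

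| Rate/yr | k | Follow-up | First-event share (reference arm) | Cox HR | Cox power | NB power |
|---|---|---|---|---|---|---|
| 0.5 | 1 | 24 weeks | 0.81 | 1.222 | 23% | 27% |
| 1 | 1 | 24 weeks | 0.68 | 1.203 | 30% | 41% |
| 0.5 | 0.5 | 1 year | 0.72 | 1.221 | 38% | 50% |
| 1 | 1 | 1 year | 0.50 | 1.178 | 36% | 58% |
| 2 | 1 | 1 year | 0.33 | 1.157 | 37% | 70% |

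Over the whole grid, the Cox analysis leaves out from about 15% of events (0.5 per year, 24 weeks, k = 0.5) to about 88% (3 per year, 2 years, k = 2). Attenuation on the log scale runs from 6% to 56%. With k near 0 the hazard ratio stays at 1.25: there is no attenuation, only a loss of precision.

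**Simplifications.** The Cox model is treated as unstratified, although the protocol calls it conditional. Censoring at switching or stopping is not modelled. The data come from the family that the negative binomial model fits, which favours that model.

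**The case against.** The strongest counter-argument is textual. A reader might infer that the all-events model is merely optional and that recurrent events are discarded. The protocol does not support that: only the annual-rate model carries the word *may*, and the total-count model is a firm commitment. Recurrent events are missing from one analysis, not from the plan. That part of the objection stands in full.

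A reader might also infer that the Cox result is the declared headline, because it comes first and is said to estimate the main effect. That is not stated either. Paragraph order is not a hierarchy, and the main effect can simply mean the coefficient for utilization pattern, since the text goes on to interactions. Nor can it be said that most events are lost or that dilution is certain. Without a stated rate, dispersion or follow-up distribution the loss could be small, and a hazard ratio and a rate ratio are in any case different quantities.

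It can further be said that reporting both kinds of analysis is reasonable in an observational registry study, and that precedence may sit in an analysis plan not shown here. Both are fair, but they do not dispose of the point. The mismatch is in what the protocol itself states: a count outcome, a firm first-event model, and an optional rate model whose own justification is the expected dispersion and the dependence on follow-up.

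One practical objection also stands. The Cox analysis has a stated censoring rule at switching and stopping, and the count models have none. Promoting a count model therefore requires its follow-up window to be settled.

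**Conclusion.** The point holds in a limited form. Section 4.2 gives three unranked analyses of the primary exacerbation outcome. The firm first-listed one does not match the Table 3 count, the one that does match is optional, and the firm count model lacks a stated follow-up adjustment.

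Under the heterogeneity that the protocol expects, the first-event hazard ratio lies nearer to 1 than the rate ratio, and the Cox analysis has less power than the count model on the same patients. The direction follows from that expectation. The size rests entirely on the assumed rate, dispersion, effect and group size: about 22 percentage points of power in the central case and about 4 at 0.5 per year over 24 weeks with the same dispersion. It is worth correcting before results are interpreted, but it does not show that the plan discards recurrent events.

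**What to change.** In section 4.2:

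- Name one primary analysis of exacerbations: a negative binomial model of the event count with log follow-up time as offset. This single statement replaces both the optional annual-rate model and the separate total-count model.
- Make the Kaplan-Meier curves and the Cox model of time to first exacerbation supportive.
- State the follow-up window for the count model and how time after switching or stopping is handled, consistently with how the utilization groups are defined.
- Apply the same order to the hospital and emergency room counts in the health resource utilization paragraph.

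The cost is mainly protocol wording, because Table 3 already defines the count and the model is already foreseen. There are two small downsides: the hazard ratio is no longer a candidate for the headline result, and the count model's follow-up window has to be decided and written down.
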